2.5.2 Data handling conventions for secondary efficacy variables

Scheduled measurements (see [Section 2.5.4](#)) of continuous efficacy variables collected during the study will be used in the analyses including those obtained after IMP discontinuation or introduction of rescue therapy. Continuous secondary efficacy endpoints will be analyzed with missing values imputed by the retrieved dropouts imputation method or by the washout imputation method according to the criterion described in [Section 2.4.4.1](#).

For the categorical secondary efficacy endpoints, data handling conventions are described in [Section 2.4.4.2](#).

2.5.3 Missing data

For categorical variables, patients with missing data are not included in calculations of percentages unless otherwise specified. When relevant, the number of patients with missing data is presented.

Derived variables will be considered missing if any of the original variables required to calculate them are missing. For example, if either a baseline assessment or an endpoint assessment is missing for a particular patient, then change from baseline at endpoint will be missing. Depending upon the assessment, analyses may not include all patients in the analysis population, because certain patients in the intended population may have missing data.

Incomplete date of first administration of double-blind IMP

Date/time of first administration is the first non-missing start date/time of double-blind IMP completed in the e-CRF “First dose IMP” module.

For patients who are randomized and dispensed a double-blind treatment kit but who are lost to follow-up just after Visit 6 (eg. only the treatment kit number is reported in the e-CRF “Exposure

- treatment period” module without any dose information), the date of first administration will be imputed using the date of randomization. When a patient is randomized but not exposed, “Not taken” should be ticked in the e-CRF “First dose IMP” module.

Handling of computation of treatment duration if IMP end of treatment date is missing

For the calculation of the treatment duration, the date of the last dose of double-blind IMP is equal to the date of last administration reported on the e-CRF “Treatment status library” page. If this date is missing, the exposure duration should be left as missing.

The last dose administration should be clearly identified in the case report form and should not be approximated by the last returned package date.

Handling of medication missing/partial dates

No imputation of medication start/end dates or times will be performed. If a medication date or time is missing or partially missing and it cannot be determined whether it was taken prior or concomitantly, it will be considered a prior, concomitant, and post-treatment medication.

Handling of adverse events/hypoglycemia with missing or partial date/time of onset

Missing or partial adverse event/hypoglycemia onset dates and times will be imputed so that if the partial adverse event/hypoglycemia onset date/time information does not indicate that the adverse event/hypoglycemia started prior to treatment or after the treatment-emergent adverse event period, the adverse event/hypoglycemia will be classified as treatment-emergent. No imputation of adverse event end dates/times will be performed. These data imputations are for categorization purpose only and will not be used in listings. No imputation is planned for date/time of adverse event resolution.

Handling of adverse events/hypoglycemia when date and time of first IMP administration is missing

When the date and time of the first double-blind IMP administration is missing, the day of randomization should be considered as the start date of TEAE period (see [Section 2.1.4](#)). The exposure duration should be kept as missing.

Handling of adverse events/hypoglycemia when IMP end of treatment date is missing

For the purpose of defining TEAE period, the date of the last administration of double-blind IMP is equal to the date of the last administration reported on the eCRF “Treatment Status Library” page.

If the date of last administration reported on the eCRF “Treatment Status Library” page is

- Partially missing, it will be imputed with a date as late as possible before or on the date of last available information on eCRF “Completion of End of Study/Follow-up”.

- Completely missing, it will be imputed with the date of last available information on eCRF “Completion of End of Study/Follow-up” page.

If the date of last available information on eCRF “Completion of End of Study/Follow-up” page is

- Partially missing, it will be imputed with a date as late as possible.
- Completely missing, all adverse events occurred on or after the first administration of double-blind IMP will be considered as treatment emergent adverse events.

Handling of missing assessment of relationship of adverse events to IMP

If the assessment of the relationship to IMP is missing, the relationship to IMP has to be assumed and the adverse event considered as such in the frequency tables of possibly related adverse events, but no imputation should be done at the data level.

Handling of missing severity/grades of adverse events

If the severity/grade is missing for 1 of the treatment-emergent occurrences of an adverse event, the maximal severity on the remaining occurrences will be considered. If the severity is missing for all the occurrences, a “missing” category will be added in the summary table.

Handling of potentially clinically significant abnormalities

If a patient has a missing baseline he will be grouped in the category “normal/missing at baseline.”

For PCSAs with 2 conditions, one based on a change from baseline value or a normal range and the other on a threshold value, with the first condition being missing, the PCSA will be based only on the second condition.

For a PCSA defined on a threshold and/or a normal range, this PCSA will be derived using this threshold if the normal range is missing; eg, for eosinophils the PCSA is > 0.5 GIGA/L or $>ULN$ if $ULN \geq 0.5$ GIGA/L. When ULN is missing, the value 0.5 should be used.

Measurements flagged as invalid by the laboratory will not be summarized or taken into account in the computation of PCSA values.

Linked adverse events that worsened or became serious

An AE that worsened or became serious will have a separate record in the data from the original event record with an AE identification number that links the new record to the original record. An AE that worsened or became serious will be considered a new recurring AE in the summary of recurrent events or in the summary of events by time intervals.

Handling of missing data for continuous efficacy endpoints

Please see [Section 2.4.4.1](#) and [Section 2.4.4.2](#).

Handling of missing data for categorical secondary efficacy endpoints

Please see [Section 2.4.4.2](#).

2.5.4 Windows for time points

The following steps will decide how the scheduled and/or unscheduled visits will be used in the analyses on efficacy variables and the by-visit summaries for safety variables (clinical laboratory data in [Section 2.1.5.2](#) and vital signs in [Section 2.1.5.3](#)).

Step 1 A scheduled measurement will be used if it is available; otherwise, an unscheduled measurement (including the end of treatment/study visit for those prematurely discontinued) will be used if it happens to be on the same date as the date of the scheduled visit.

Step 2 After Step 1, if there are still no measurement for a given parameter at a scheduled visit, the analysis window below ([Table 6](#)) will be applied to re-allocate a post-baseline unscheduled measurement to a scheduled measurement.

Table 6 - Analyses window definition

Scheduled visit post baseline	Targeted study day	Analysis window in study days
Week 4 (Visit 8)	28	2 to 41
Week 8 (Visit 10)	56	42 to 69
Week 12 (Visit 11)	84	70 to 104
Week 18 (Visit 12)	126	105 to 153
Week 26 (Visit 13)	182	154 to 227
Week 39 (Visit 14)	273	228 to 318
Week 52 (Visit 15)	364	≥319

Study days are calculated from the day of first administration of double-blind IMP; the day of first administration of IMP (or the day of randomization if not exposed) is Day 1.

After applying the above time windows, if multiple assessments are associated to the same time point, the closest from the targeted study day will be used. In case of equality, the last measurement will be used. Re-allocated scheduled visits (ie, visit numbers) should be sequential if ordered by the date of measurement.

After Step 2, if there are still no measurement for a given parameter at a scheduled visit, data is considered missing for efficacy analyses, where multiple imputation would be applied as appropriately as described in [Section 2.4.4](#).

Reference day

The reference day for the calculation of extent of exposure, time to onset, and relative days will be the day of the first administration of double-blind IMP or the day of randomization if not exposed to double-blind IMP, denoted as Day 1.

Baseline definition for efficacy/safety data

For the safety analyses, the baseline for a given parameter is defined as the last available measurement (or the average of all measurements for creatinine and eGFR), including unscheduled assessments, assessed prior to the first administration of double-blind IMP. For the efficacy analyses, the baseline for a given parameter is defined as the last available measurement (or the average of all measurements for creatinine and eGFR), including unscheduled assessments, assessed prior to the first administration of double-blind IMP or the last available value (or the average of all measurements for creatinine and eGFR) before randomization if not treated with double-blind IMP.

Summary statistics by visit for continuous efficacy endpoints

Summary statistics (number, mean, SD, SE, minimum, median, maximum) of continuous efficacy endpoints (observed data and change from baseline) will be provided at scheduled visits as per protocol. Summaries showing data by visit will be presented according to the visit number (or re-allocated visit number, see [Section 2.5.4](#)) and labeled with the targeted approximate day/week.

Last on-treatment value for laboratory variables and vital signs

The last on-treatment value is the final measurement assessed during the treatment epoch, regardless of the introduction of rescue therapy, including measurements at unscheduled visits. Please see details in [Section 2.1.4](#) and [Section 2.4.5](#)

Display of safety data by visit (laboratory variables and vital signs)

Descriptive statistics (number, mean, SD, minimum, median, maximum) of quantitative laboratory variables and vital signs (observed data and change from baseline) during the TEAE period will be provided at scheduled visits. In addition, these summaries will also include a row for the 'last value on-treatment' to describe the last available on-treatment value (see above). Summaries showing data by visit will be presented according to the visit number (or re-allocated visit number, see [Section 2.5.4](#)) and labeled with the targeted approximate day/week.

As specified in the study protocol, laboratory data from scheduled visits are reported by central laboratories. The local results will not be used in the efficacy analyses or in the definition of baseline for both safety and efficacy analyses. In the safety analyses, local results will only be used in the PCSA summary if they are accompanied by a local laboratory normal range.

When a patient has more than 1 measurement from the central laboratory for the same laboratory parameter on the same date, the average of the measurements will be used. For the same laboratory parameter, if a patient has more than 1 measurement on different dates for the same

scheduled visit, the value closest to the date of the visit will be used for the scheduled visit. When the values for the same scheduled visit are equidistant, the last value should be used for the scheduled visit. Similar rules will be applicable to a patient who has more than 1 set of measurements for the same vital sign parameter (ie, SBP, DBP, or HR) on the same date.

Time to event analysis

For time to event analysis/KM plot, time to event (eg, treatment discontinuation, rescue therapy, hypoglycemia, etc) is defined as the number of days from the date of the first administration of double-blind IMP (or the date of randomization if not exposed) to the start date of the first occurrence of the event during entire 52-week double-blind treatment period.

Patients who did not experience any event during the entire 52-week double-blind treatment period are considered censored observations. For treatment discontinuation and time to rescue, censoring date is the date of EOT. For time to severe or documented hypoglycemia, censoring date is date of EOT+1 or date of EOS, whichever is the earliest. Date of EOS will be used if date of EOT is not available. Last contact date will be used if date of EOS is not available.

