8.7.2 Return and/or destruction of treatments

Patients are to return all IMP and Lantus NIMP (unused, in-use, or used wallets and pens) at each on-site visit (or final assessment on-treatment visit, in the case of permanent premature discontinuation), as described in [Section 1.2](#)). IMP accounting is not required at telephone visits.

Patients are to return all IMP and Lantus NIMP (unused, in-use, or used wallets and pens) at Visit 15 (or final assessment on-treatment visit, in the case of permanent premature discontinuation).

All used wallets and pens, partially-used, or unused IMPs, and basal Lantus NIMP will be retrieved by the sponsor or delegate. A detailed site and patient treatment log of the returned IMP and basal Lantus NIMP will be established with the Investigator and countersigned by the Investigator and the monitoring team.

For NIMP not provided by the Sponsor (ie, metformin or other OAD), tracking and reconciliation is to be undertaken by the Investigator (or pharmacist if appropriate) according to the system proposed by the CRO.

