9.2 SAFETY ENDPOINTS

Assessments for safety include AEs, SMBG, clinical laboratory assessments, physical examination, 12-lead ECG, weight, and vital signs. An independent DMC will meet on a regular basis to review accumulating clinical trial safety data.

Adjudication of all deaths, MACE/other selected CV events, selected renal events, bone fracture, and DKA will be performed in a blinded manner by a CEC(s) comprised of experts. Details will be provided in the charter of the CEC(s). Further details are available in [Section 6.3.3](#).

Two expert committees will review all potential cases of DILIs and cases of amputation in a treatment-blinded manner.

The following safety endpoints will be assessed throughout the 52-week double-blind Treatment Period:

- Adverse events, AEs leading to discontinuation from the IMP, adverse events of special interest (AESI), EOSI, SAEs, and deaths
- Hypoglycemia (all, severe and/or documented symptomatic)
- Markers of calcium metabolism
- Safety laboratory results (including amylase, lipase, and fasting lipids; see [Section 9.2.1.3](#)), vital signs results, and 12-lead ECG results.

Observation period of safety endpoints

The observation period of safety data will be divided into 3 segments:

- The pre-Treatment Period is defined as the time between the date of informed consent and the first dose of double-blind IMP.
- The on-Treatment Period (TEAE period) is defined as the time from the first dose of double-blind IMP up to 10 days (1 day for hypoglycemia) after the last dose of double-blind IMP, regardless of the introduction of rescue therapy. The 10-day interval is chosen based on the half-life of the IMP (approximately 5 times the half-life of sotagliflozin) in patients with moderate renal dysfunction.
- The post-Treatment Period is defined as the time starting 11 days after the last dose of double-blind IMP (after the on-Treatment Period).

The Baseline value for safety endpoints in the safety population is the last available value (or the average of all values for creatinine or eGFR) prior to the first administration of the double-blind IMP.

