10.3.3 List of criteria for permanent treatment discontinuation

Patients may withdraw from treatment with the IMP at any time for any reason or this may be the Investigator's decision. Patients should discuss stopping study medication with the site before doing so in order that questions can be addressed, glycemic therapy adjusted, and a follow-up assessment arranged. All efforts should be made to document the reasons for treatment discontinuation and this should be documented in the eCRF.

The following reasons lead to permanent discontinuation:

- At the patient's own request (ie, withdrawal of consent for treatment)
- If, in the Investigator's opinion, continuation with the administration of the study treatment would be detrimental to the patient's well-being

- Intercurrent condition that requires permanent discontinuation of the study treatment as long as the abnormality persists and if the causal relationship of the concerned event and the IMP is possible (according to the Investigator's best medical judgment)
- Pregnancy (in female patients)
- Specific request of the Sponsor.

Any abnormal laboratory value will be immediately rechecked to confirm the result before a decision is made to permanently discontinue IMP for the concerned patient.

For patients who prematurely discontinue the IMP, the assessments planned at the EOT Visit (see [Section 10.1.2.3](#)) will be performed at the Premature EOT Visit scheduled preferably prior to treatment discontinuation or as soon as possible after the time of discontinuation (at the latest at the next scheduled on-site visit). In the case of premature IMP discontinuation, PK samples should not be drawn at the Premature EOT Visit, or at any subsequent visit. The reason(s) for IMP discontinuation will be clearly specified. This EOT assessment may occur at a regularly scheduled or unscheduled visit.

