11.4.3 Analyses of safety data

The summary of safety results will be presented by treatment group. All safety summaries will be descriptive; no statistical significance tests will be performed on safety data.

Safety endpoints are presented in [Section 9.2](#). These analyses will be based on the safety population as defined in [Section 11.3.3](#). Patients will be analyzed for safety analyses according to the treatment actually received. The safety analyses will be provided for the 18-week randomized core Treatment Period and for the entire 52-week double-blind Treatment Period, unless specified otherwise.

The following definitions will be applied to laboratory parameters and vital signs:

- The potentially clinically significant abnormality (PCSA) values for clinical laboratory tests and vital signs are defined as abnormal values considered medically important by the Sponsor's Global Pharmacovigilance and Epidemiology department and in effect at the time of the final SAP approval. The PCSA criteria for parameters not cited in the protocol as safety parameters will not be analyzed.
- The PCSA criteria will determine which patients had at least 1 PCSA during the on-treatment period, taking into account all evaluations performed during the on-treatment period, including unscheduled or repeated evaluations. The number of all such patients will be the numerator for the on-treatment PCSA percentage.

The "observation periods" defined in [Section 9.2](#) are applicable for classification of AEs, determination of on-treatment PCSA values and the last on-treatment value for the laboratory, vital sign and ECG parameters.

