2.1.4 Safety endpoints

The safety analysis will be based on the reported adverse events, hypoglycemia, and other safety information, such as clinical laboratory data, vital signs, electrocardiogram (ECG), and physical examination, etc.

Observation period

The observation period will be divided into 4 epochs:

- The **screening** epoch is defined as the time from the signed informed consent date up to the first administration of the double-blind IMP.
- The **treatment** epoch is defined as the time from the first administration of the double-blind IMP to the last administration of the double-blind IMP.

- The **residual treatment** epoch is defined as the time from the last administration of the double-blind IMP up to 10 days (1 day for hypoglycemia) after the last administration of the double-blind IMP.

The treatment-emergent adverse event (TEAE) period will include both **treatment** and **residual treatment** epochs (see the TEAE period of the 18-week randomized core treatment period for analyses in hypoglycemia in [Section 2.4.5.1](#)).

- The **posttreatment** epoch is defined as the period of time starting the day after the end of the treatment-emergent adverse event period up to the last protocol-planned visit or the resolution/stabilization of all serious adverse events (SAE), adverse events of special interest (AESI) and events of special interest (EOSI), whichever is later.

The on-study observation period is defined as the time from start of double-blind treatment until the end of the study (defined as the last scheduled visit for those who completed the study and the date collected on e-CRF page “Completion of End of Study/Follow-up” for those who did not complete the study).

The post-study observation period is defined as the time from the day after the end of the study until the resolution/stabilization of all SAE, AESI and EOSI if applicable.

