- For quantitative safety parameters based on central laboratory/reading measurements, descriptive statistics will be used to summarize results and change from baseline values by visit and treatment group for the entire 52-week double-blind treatment period only. Summaries will include the last on-treatment value. The last on-treatment value is commonly defined as the value collected at the same day/time of the last administration of

IMP. If this value is missing, this last on-treatment value will be the closest value prior to the last dose administration of IMP during the entire 52-week treatment period.

- The analysis of the safety variables will be essentially descriptive and no systematic testing is planned. Relative risks versus placebo and their 95% confidence intervals may be provided, if relevant
- Selected safety analyses will be summarized by age, gender, racial subgroups, and any pertinent subgroups (see details in [Section 2.4.5.1](#) and [Section 2.4.5.2](#)).

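### The SAP ends the last on-treatment laboratory and vital-sign value at the last dose, whereas the protocol runs it to 10 days after; this matters mainly for early stoppers sampled in those 10 days

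*SAP*

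**What the plan says.** **Protocol.** Section 9.2 defines the on-treatment period as the "time from the first dose of double-blind IMP up to 10 days (1 day for hypoglycemia) after the last dose of double-blind IMP". It bases the 10 days on about five half-lives in patients with moderate renal dysfunction. Section 11.4.3 applies the Section 9.2 periods to, among other things, the "determination of on-treatment PCSA values and the last on-treatment value for the laboratory, vital sign and ECG parameters".

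**SAP.** Section 2.1.4 splits the same span in two. The treatment epoch is "the time from the first administration of the double-blind IMP to the last administration of the double-blind IMP". A separate residual epoch covers the next 10 days, and the two together form the TEAE period. Section 2.4.5 first points to the Section 2.1.4 observation period in general, then takes the value from the day and time of the last administration. It continues: "If this value is missing, this last on-treatment value will be the closest value prior to the last dose administration of IMP". Section 2.5.4 states the rule that covers both laboratory and vital-sign data: "The last on-treatment value is the final measurement assessed during the treatment epoch, regardless of the introduction of rescue therapy", with unscheduled visits counted.

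**Timing of the sample.** Protocol 10.3.3 prefers the Premature EOT Visit before the patient stops. Failing that, it is to be held "as soon as possible after the time of discontinuation (at the latest at the next scheduled on-site visit".

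**The concern.** The protocol counts a sample taken 1 to 10 days after the last dose as on-treatment. The SAP excludes it from the last on-treatment row and puts an older value there. For a patient who stops because of an event, the excluded sample may be the one nearest the event.

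The two periods also meet inside one table. SAP 2.5.4 builds the by-visit laboratory and vital-sign statistics on the TEAE period and adds the last on-treatment row to the same summaries under the shorter epoch. A sample can therefore appear in a visit row while the row labelled as last shows an earlier visit.

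SAP Tables 1 and 2 (Sections 1.5 and 1.6) list no such change in their legible rows. Some Table 2 rows are redacted, so a declaration there cannot be excluded.

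**Working it through.** The plan states no figure for this point, so there is none to reproduce. The check has four steps.

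**1. Where the rules differ.** Let L be the day of the last dose and L + k the day of the end-of-treatment sample.

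| k | Protocol 11.4.3 with 9.2 | SAP 2.5.4 and 2.4.5 |
|---|---|---|
| 0 | on-treatment | on-treatment |
| 1 to 10 | on-treatment | excluded; nearest earlier value used |
| 11 or more | off-treatment | off-treatment |

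Only k = 1 to 10 separates them.

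**2. How old the substitute is.** Inputs are the target days in SAP Table 6 (Week 12 = 84, Week 18 = 126, Week 26 = 182, Week 39 = 273, Week 52 = 364), the sampling schedule in Protocol 1.2 and 10.1.2, and the visit windows (±3 days through Visit 13, ±7 days for Visits 14 and 15). The longest nominal gap between consecutive scheduled samples is:

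- Clinical chemistry and vital signs: 364 − 273 = 91 days (Week 39 to 52). The windows add or subtract 7 + 7 = 14, giving 77 to 105. Week 26 to 39 is also 273 − 182 = 91. BHB skips Week 12, but its longest gap is the same 91.
- Hematology (Weeks 0, 12, 26, 39, 52): 182 − 84 = 98 days (Week 12 to 26). The windows add or subtract 3 + 3 = 6, giving 92 to 104.
- Fasting lipids (Weeks 0, 18, 52): 364 − 126 = 238 days. The windows add or subtract 3 + 7 = 10, giving 228 to 248.

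These are upper ends. An unscheduled on-drug sample shortens the lag. A patient who stops before Week 12 (hematology) or Week 18 (lipids) and is sampled after the last dose has no post-baseline value in this row, unless an unscheduled sample was taken on drug.

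**3. Illustration (hypothetical patient).** Last dose on Day 180, Premature EOT sample on Day 182, so k = 2. Under the protocol the last on-treatment hemoglobin is the Day 182 value. Under the SAP it is the Week 12 value, nominally Day 84, which is 98 days older. The Day 182 value still enters the Week 26 row, because it lies in the Day 154 to 227 analysis window and before the TEAE period ends on Day 190.

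**4. Drug remaining.** In moderate renal dysfunction, 10 days ÷ 5 gives a half-life of about 2 days. The fraction left is 2^(−1/2) = 0.71 after 1 day, 2^(−1) = 0.50 after 2 days and 2^(−5) = 0.03 after 10 days. For other patients, assume a half-life of about 1 day, from the 5-day figure that SAP Table 1 records as replaced. The fractions are then 0.50, 0.25 and 2^(−10) = 0.001.

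**The case against.** The narrower rule can be defended on its merits. SAP 2.1.4 separates the treatment and residual epochs on purpose. It is coherent to use the wide period for treatment-emergent abnormalities and the narrow one for a mean that describes patients on drug, since little drug remains late in the 10 days. That would support choosing the SAP rule openly. It does not support replacing a rule the protocol already set without saying so.

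The affected group is also limited. The Premature EOT Visit is preferably held on drug. Protocol 10.3.3 requires an abnormal laboratory value to be rechecked before a decision to stop permanently, and an on-drug central-laboratory recheck counts under SAP 2.5.4 and 2.5.5. No data are lost either, because the by-visit and PCSA summaries use the TEAE period. All of this stands.

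Two stronger readings are tempting, and the documents support neither.

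- **That completers' Week 52 values are replaced by Week 39 values.** A reader might infer this because laboratory samples are pre-dose and Protocol 8.7.2 says "Patients are to return all IMP and Lantus NIMP (unused, in-use, or used wallets and pens) at Visit 15". But Visit 16 is planned for Day 378, two weeks after the last dose, and 378 − 14 = 364, so the planned last dose falls on the Visit 15 day. Protocol Table 5 labels the Week 52 pharmacokinetic sample as pre-dose, which presupposes a dose that day. SAP 2.4.5 accepts a same-day value, so an on-schedule Week 52 sample is captured. The return of tablets settles nothing, since the Visit 15 list in Protocol 10.1.2.3 also asks for wallets back at the next visit. Only a completer who takes no dose on the Visit 15 day is affected.
- **That 71% or 50% of drug remains in every patient 1 or 2 days after the last dose.** Those figures hold only for the half-life implied for moderate renal dysfunction.

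**Conclusion.** The contradiction between Protocol 11.4.3 with 9.2 and SAP 2.4.5 with 2.5.4 is explicit and should be corrected. Its reach is modest. It alters one descriptive safety row, and it touches no test and no efficacy endpoint. Within that row, a value can be nominally 91, 98 or 238 days older than the sample the protocol would use, depending on the parameter, or can be absent.

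This rests on some end-of-treatment samples falling 1 to 10 days after the last dose with no later on-drug sample available. The visit rules allow that, but the documents do not say how often it will happen, so the number of patients cannot be derived.

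**What to change.** In SAP 2.5.4 and 2.4.5, define the last on-treatment value as the last value from first dose through the end of the TEAE period (last dose + 10 days), as Protocol 11.4.3 provides. Delete from 2.4.5 the condition that the value be from the day and time of the last dose, and the sentence that falls back to the closest earlier value. If the narrower rule is intended, declare it in SAP 1.6 as a departure from Protocol 11.4.3 and give the reason.

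The cost is SAP wording and one date condition in the code. On-schedule follow-up samples stay out: Visit 16 falls 14 ± 3 days after the last dose, so no earlier than 14 − 3 = day 11. The small downside is that values late in the 10-day window reflect partial washout.
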